7.2.4. Effectiveness Analysis

7.2.4.1. Success Rate of MAC Prevention in Patients Treated for the Prevention of MAC Infection

Using the (preventive) effectiveness analysis set, the numbers of patients with and without occurrence of MAC infection will be counted, and the number and percentage of patients without MAC infection will be calculated as the success rate of MAC prevention. If a single patient received multiple prophylactic treatments, the patient is counted as many times as the number of the prophylactic treatments the patient received. The percentage will be calculated using the total number of preventive treatments in the analysis set as the denominator, and the 95% CI of the percentage will also be calculated. If there is a case of multiple prophylactic treatments in a single patient, the number of patients who never experienced MAC infection will be counted, and the percentage and its 95% CI will be calculated as the patient-based success rate of MAC prevention.

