3. HYPOTHESIS AND DECISION RULES

3.1. Statistical Hypothesis

Because this study is not a confirmatory investigation, the tests are considered exploratory and a p-value resulting from a test will be considered as a descriptive statistic with no significance level specified, although a post-hoc threshold value may be introduced for a screening purpose.

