- Baseline CD4 count (cells/mm³) [≥0 to <100, ≥100 to <200, ≥200 to <350, ≥350 to <500, ≥500]
- Centers for Disease Control and Prevention (CDC) classification [A, B, C, P-0, P-1, P-2]

Subgroup analyses of effectiveness will also be performed for the following other factors:

- Maximum daily dose [<150 mg, 150 mg, 300 mg, 450 mg, >450 mg]
- Mean daily dose [<150 mg, 150 mg, >150 mg to <300 mg, 300 mg, >300 mg to <450 mg, 450 mg, >450 mg]
- Duration of one prophylactic or therapeutic treatment [≤1 week, >1 week to ≤2 weeks, >2 weeks to ≤4 weeks, >4 weeks to ≤8 weeks, >8 weeks to ≤12 weeks, >12 weeks to ≤24 weeks, >24 weeks to ≤36 weeks, >36 weeks to ≤1 year, >1 year]
- Concomitant medications (anti-MAC drugs) [absent, present]
- Concomitant use of SMX/TMP [absent, present]

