7.1.3. Analysis of Binary Data

Binary variables will be calculated by frequency and percentage. Confidence intervals (CIs) for the percentages may also be calculated; in this case, the 95% CIs (two-sided) will be calculated using an exact method. Statistical tests may also be performed when appropriate; an association with a nominal variable will be tested by Fisher's exact test, and an association with an ordinal variable by the exact Cochran-Armitage test.

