7.2. Statistical Analysis

7.2.1. Overview of Patients

- **Number of sites by establisher and number of patients**

In patients for whom the case report form was collected, the number and percentage of sites by establisher shown below and the number and percentage of patients will be calculated:

- University hospitals
- National hospitals established by the Ministry of Health, Labour and Welfare
- Prefectural and municipal hospitals
- Public organizations
- Hospitals established by corporations and individuals other than the above four
- General practitioners/clinics

In addition, the mean, minimum, and maximum of the number of patients per site will be calculated.

- **Disposition of patients**

In the patients for whom the case report form was collected, the number of those for whom the case report form was collected and those included in the safety analysis set will be tabulated. The patients excluded from the safety analysis set will also be counted in total and by reason for exclusion. In addition, Among the safety analysis set, the patients who are eligible for the effectiveness analysis will be counted for each of preventive and therapeutic treatments. The patients excluded from the effectiveness analysis set will also be counted in total and by reason for exclusion for each of preventive and therapeutic treatments. Total number of treated patients will be counted in a treatment-based manner for each of preventive and therapeutic treatments, because in this investigation, cases of multiple treatments in a single patient are expected to occur.

- **Listing of excluded patients**

Patients excluded from the safety analysis set and those excluded from the effectiveness analysis set will be tabulated with their reason for exclusion.

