7.2.4.2. Clinical efficacy (overall improvement)

Using the (therapeutic) effectiveness analysis set, the number of patients falling into each category of clinical efficacy (overall improvement) will be counted, and the clinical response rate (improvement rate) defined in the formula below and its 95% CI will be calculated. Because a single patient can be infected and treated multiple times during the survey period, patients are counted in a treatment-based manner, i.e., they are counted as many times as the number of the treatments they received. If there is a case of multiple therapeutic treatments in a single patient, the clinical response rate (improvement rate) at the final observation point defined in the formula below, and its 95% CI will also be calculated.

$$\text{Clinical response rate (improvement rate) based on total number of cases (\%)} = \frac{(\text{Total number of markedly improved cases} + \text{Total number of improved cases})}{(\text{Total number of cases eligible for the therapeutic effectiveness analysis except indeterminable cases})} \times 100$$

$$\text{Clinical response rate (improvement rate) at the final observation point (\%)} = \frac{(\text{Numbers of markedly improved patients at the final observation point} + \text{Numbers of improved patients at the final observation point})}{(\text{Number of patients eligible for the therapeutic effectiveness analysis except indeterminable patients at the final time point})} \times 100$$

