7.2.4.4. Subgroup Analysis

Subgroup analyses of the success rates of MAC prevention, clinical response rates (improvement rate), and eradication rates will be performed for each of the factors listed in Section 4.5.

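### The 95% CIs on the three per-course effectiveness rates treat repeat courses in one patient as independent, and may be too narrow if outcomes correlate within patients

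*SAP*

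**What the plan says.** - **Unit of counting.** In SAP 7.2.4.1 a patient with several prophylactic courses contributes each of them, and the success rate is calculated "using the total number of preventive treatments in the analysis set as the denominator, and the 95% CI of the percentage". For clinical response (7.2.4.2) and eradication (7.2.4.3), "patients are counted in a treatment-based manner, i.e., they are counted as many times as the number of the treatments they received". Each of these rates gets a 95% CI, and 7.2.4.3 repeats the eradication analysis by reason for use.
- **Interval method.** SAP 7.1.3 offers one: "the 95% CIs (two-sided) will be calculated using an exact method". No section mentions clustering, robust variance or resampling by patient.
- **Repeats foreseen.** SAP 7.2.1 counts courses because "cases of multiple treatments in a single patient are expected to occur".
- **Per-patient companions.** If repeats occur, 7.2.4.1 adds the proportion of patients who never had MAC infection: "the percentage and its 95% CI will be calculated as the patient-based success rate of MAC prevention". Sections 7.2.4.2 and 7.2.4.3 add rates at the final observation point, also with CIs.
- **Subgroups.** SAP 7.2.4.4 says the analyses of all three rates "will be performed for each of the factors listed in Section 4.5", without giving the unit. One effectiveness factor in 4.5, "Duration of one prophylactic or therapeutic treatment", is a property of a course, not of a patient.

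**The concern.** An exact binomial interval is valid for independent trials. Two courses in the same patient share the host, the immune status and often the organism, so their outcomes are likely to be positively correlated. The SAP adapts its counting to repeat courses but not its variance. With positive correlation the number of courses overstates the information and the printed interval is too narrow; negative correlation would make it too wide. With no confirmatory test planned, the rates and their intervals are the main effectiveness output of the final analysis for reexamination (SAP 2), so their stated precision should be right.

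**Working it through.** The plan gives no sample size, expected rate, repeat share or within-patient correlation, so there is no figure of its own to reproduce. The check shows how far the interval could be off.

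**Inputs from the SAP:** two-sided 95% exact limits (7.1.3), taken here as Clopper–Pearson; n = number of courses (7.2.4.1–7.2.4.3).

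**Assumed inputs:** 100 patients; true success rate 0.6, 0.7 or 0.9; within-patient correlation ρ of 0, 0.3, 0.5 or 0.6 (beta-binomial); four repeat patterns.

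**Step 1: design effect.** With mᵢ courses in patient i,

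DEFF = 1 + (Σmᵢ² / Σmᵢ − 1) × ρ; effective n = Σmᵢ / DEFF; required width ≈ √DEFF × unadjusted width.

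| Pattern (100 patients) | Σm | Σm² | DEFF at ρ = 0.5 | DEFF at ρ = 0.6 |
|---|---|---|---|---|
| 10 with 2 courses | 110 | 130 | 1.09 | 1.11 |
| 20 with 2 courses | 120 | 160 | 1.17 | 1.20 |
| 20 with 2, 20 with 3 | 160 | 320 | 1.50 | 1.60 |
| 30 with 4 courses | 190 | 550 | 1.95 | 2.14 |

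Example, third row at ρ = 0.5: 1 + (320/160 − 1) × 0.5 = 1.50; effective n = 160/1.50 = 106.7.

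**Step 2: coverage of the unadjusted nominal 95% interval** (range over the three rates)

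| Pattern | ρ = 0 | ρ = 0.3 | ρ = 0.5 | ρ = 0.6 |
|---|---|---|---|---|
| 10–20 with 2 courses | at least 95% | 95–97% | 94–97% | 94–97% |
| 20 with 2, 20 with 3 | at least 95% | 92–94% | 90–92% | 89–91% |
| 30 with 4 courses | at least 95% | 89–90% | 85–86% | 83–84% |

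Exact methods are conservative, and with few repeats this absorbs most of the loss.

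**Step 3: limits for an observed 70% at ρ = 0.5**

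| Courses | Unadjusted | On effective n |
|---|---|---|
| 84/120 | 61.0–78.0% | 60.2–78.6% (n = 102.9) |
| 112/160 | 62.3–77.0% | 60.4–78.5% (n = 106.7) |
| 133/190 | 62.9–76.4% | 59.9–78.9% (n = 97.6) |

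**Step 4: can the per-patient rate stand in?** Take 90% success per course, ρ = 0.5 and the third pattern. The beta parameters are 0.9 and 0.1. All courses succeed with probability 0.9 for one course, 0.9 × 1.9/2 = 0.855 for two, and 0.855 × 2.9/3 = 0.8265 for three. The expected proportion of patients who never have MAC infection is 0.6 × 0.9 + 0.2 × 0.855 + 0.2 × 0.8265 = 87.6%, not 90%. The two rates have different targets, so an interval for one is not an interval for the other.

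**Step 5: does the remedy work?** The design effect was estimated as cluster-robust variance over binomial variance, floored at 1, and exact limits were taken on n / DEFF. In simulation (20,000 replicates per scenario, 100 patients, rates 0.6 and 0.9) coverage was 94.5–97.6%. Limits were 1–3% wider at ρ = 0 and about 23–47% wider in the two heavy-repeat patterns at ρ = 0.5–0.6.

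**The case against.** The strongest reply is that the plan largely covers itself: as soon as any patient has a repeat course, a one-record-per-patient rate with its own CI is added, so the report would not rest on the per-course interval alone. Those intervals are sound and should stay. They do not correct the interval printed on the per-course rate, and Step 4 shows that they answer a different question.

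Second, SAP 3.1 says "Because this study is not a confirmatory investigation" and 3.2 has no decision rule. This stands and limits the severity. It does not make a 95% label accurate on an interval that covers less.

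Third, the larger losses need assumptions that the documents do not support: 85–86% coverage requires 30% of patients to have four courses at correlation 0.5. That is fair. With few repeats the effect is close to nil. In the two heavy-repeat patterns, coverage is still below nominal at correlation 0.3.

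Fourth, 7.2.4.4 mentions neither CIs nor tests, unlike the safety subgroup section 7.2.3.4, and 7.1.3 makes both optional. So clustered inference in subgroups matters only if inference is done there. The missing unit of analysis needs stating in any case.

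Fifth, if every course in a set succeeds, robust variance and a patient bootstrap collapse to zero width. This is a real practical point and needs a fallback rule, given below.

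**Conclusion.** The concern holds. The three per-course rates carry intervals that assume independent courses, while the SAP itself expects repeats within patients. The size cannot be determined from the documents: negligible if few patients have repeats, but about 3 to 12 percentage points of lost coverage if 30–40% of patients have two to four courses and correlation is 0.5–0.6 (for example 92% or 83% against 95%). These figures assume 100 patients, true rates of 0.6–0.9 and exchangeable courses within a patient. No formal conclusion depends on the intervals. It should be fixed because the correction is cheap and the figures go into the reexamination analysis.

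**What to change.** 1. In SAP 7.2.4.1–7.2.4.3, including eradication by reason for use, calculate the CI of each per-course rate with a method that allows for clustering by patient. Options are exact limits on n divided by the estimated design effect (floor 1), GEE with robust variance, or a bootstrap that resamples patients.
2. State a fallback: if all courses succeed or all fail, set the design effect to 1, which gives the plain exact interval. GEE and the bootstrap need the same fallback.
3. Keep the planned per-patient rates with exact CIs beside the per-course rates, and say that they estimate different quantities.
4. In 7.2.4.4, state for each factor whether the unit is the course or the patient. Use the clustered method for any CI or test on course counts, including the factor for duration of one course, and exact methods where there is one record per patient.

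**Cost.** SAP wording and a small amount of code, including the fallback; no new data. If there is no correlation, intervals widen by only 1–3% with 100 patients. Small subgroups still need a caveat: with 30 patients, 30% of them having four courses, a 90% rate and correlation 0.3–0.6, the adjusted limits reached 91–94% coverage, against 83–90% unadjusted.

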7.2.4.2. Clinical efficacy (overall improvement)

Using the (therapeutic) effectiveness analysis set, the number of patients falling into each category of clinical efficacy (overall improvement) will be counted, and the clinical response rate (improvement rate) defined in the formula below and its 95% CI will be calculated. Because a single patient can be infected and treated multiple times during the survey period, patients are counted in a treatment-based manner, i.e., they are counted as many times as the number of the treatments they received. If there is a case of multiple therapeutic treatments in a single patient, the clinical response rate (improvement rate) at the final observation point defined in the formula below, and its 95% CI will also be calculated.

$$\text{Clinical response rate (improvement rate) based on total number of cases (\%)} = \frac{(\text{Total number of markedly improved cases} + \text{Total number of improved cases})}{(\text{Total number of cases eligible for the therapeutic effectiveness analysis except indeterminable cases})} \times 100$$

$$\text{Clinical response rate (improvement rate) at the final observation point (\%)} = \frac{(\text{Numbers of markedly improved patients at the final observation point} + \text{Numbers of improved patients at the final observation point})}{(\text{Number of patients eligible for the therapeutic effectiveness analysis except indeterminable patients at the final time point})} \times 100$$

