4. ANALYSIS SETS

4.1. Safety Analysis Set

The safety analysis set consists of the patients who meet the inclusion criteria for this study and are confirmed to have received at least one dose of Mycobutin. However patients who have received treatment with Mycobutin before marketing (those who discontinued or completed their treatment with Mycobutin before the marketing of Mycobutin[®] 150mg Capsules) will be excluded from the safety analysis set.

4.2. (Preventive) Effectiveness Analysis Set

Among the patients in the safety analysis set, those who received Mycobutin for the prevention of MAC infection and underwent an effectiveness evaluation (determination of whether an onset of MAC infection is observed or not) comprise the (preventive) effectiveness analysis set.

4.3. (Therapeutic) Effectiveness Analysis Set

Among the patients in the safety analysis set, those who underwent at least one post-treatment effectiveness evaluation (determination of bacteriological response or clinical efficacy at the end of the observation period) comprise the (therapeutic) effectiveness analysis set.

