5.2.2. Therapeutic Treatment

- Clinical efficacy (overall improvement): After each continuous treatment or at the final fiscal year of registration (the end of observation), clinical efficacy (overall improvement) will be determined using the following categories:

1. Markedly improved
2. Improved
3. Slightly improved
4. Unchanged
5. Aggravated
9. Indeterminable

- Bacteriological response: After each continuous treatment or at the final fiscal year of registration (the end of observation), bacteriological response will be determined according to the following categories:

1. Eradicated
2. Decreased
3. Unchanged
4. Increased
9. Unknown

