6. HANDLING OF MISSING DATA

Any missing value for a laboratory parameter or effectiveness endpoint will be handled as a missing value and no imputation will be carried out.

If the seriousness, measures taken, or outcome for an AE is missing, they are counted as “unknown”.

If a date such as the onset date of an AE is missing, handling of those data will be defined in separate statistical analysis specifications prepared for the drug use investigation of Mycobutin[®] 150mg capsules.

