7.2.4.3. Bacteriological response

Using the bacteriological response analysis set, the number of patients for each of the categories of bacteriological response will be counted, and the eradication rate defined in the formula below and its 95% CI will be calculated. Because a single patient can be infected and treated multiple times during the survey period, patients are counted in a treatment-based manner, i.e., they are counted as many times as the number of the treatments they received. If there is a case of multiple therapeutic treatments in a single patient, the eradication rate at the final observation point defined in the formula below, and its 95% CI will also be calculated. A similar analysis will be performed by reason of Mycobutin use.

$$\text{Eradication rate based on total number of cases (\%)} = \frac{(\text{Total number of eradicated cases})}{(\text{Total number of cases evaluated for bacteriological response except unknown})} \times 100$$

$$\text{Eradication rate at the final observation point (\%)} = \frac{(\text{Number of eradicated patients at the final observation point})}{(\text{Number of patients evaluated for bacteriological response except unknown at the final observation point})} \times 100$$

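### Both clinical response rate denominators in SAP 7.2.4.2 keep cases that have no clinical rating, so a case with bacteriology only counts as a clinical non-responder

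*SAP*

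**What the plan says.** - **Entry to the set (SAP 4.3).** One post-treatment evaluation is enough, and it may be of either kind: "determination of bacteriological response or clinical efficacy at the end of the observation period".
- **Clinical endpoint (SAP 5.2.2).** After each continuous treatment or at the end of observation, "clinical efficacy (overall improvement) will be determined using the following categories". Codes 1 to 5 run from markedly improved to aggravated, and code 9 is indeterminable. There is no code for a case that was not assessed.
- **Clinical response rate (SAP 7.2.4.2).** The numerator is markedly improved plus improved. The treatment-based denominator is the "Total number of cases eligible for the therapeutic effectiveness analysis except indeterminable cases". The patient-based denominator is the "Number of patients eligible for the therapeutic effectiveness analysis except indeterminable patients at the final time point".
- **Eradication rate (SAP 7.2.4.3).** Its denominator is the "Total number of cases evaluated for bacteriological response except unknown", and it is computed in a separate analysis set that requires a bacteriological determination (SAP 4.4).
- **Missing data (SAP 6).** "Any missing value for a laboratory parameter or effectiveness endpoint will be handled as a missing value and no imputation will be carried out".
- **Subgroups (SAP 7.2.4.4).** Analyses of the "clinical response rates (improvement rate), and eradication rates will be performed for each of the factors listed in Section 4.5".

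**The concern.** The entry rule and the denominator do not match. A patient can enter the therapeutic set on bacteriology alone, yet the clinical denominator removes only cases rated indeterminable. A case with no clinical rating is missing, which is not the same as code 9. Under the formula as written it is kept, and it has the same effect on the rate as a treatment failure. Further courses without a rating, in a patient who qualified through another course, may be kept in the same way, depending on how eligible cases are read.

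The clinical response rate and its 95% CI are reported results of the survey, which supports the reexamination application. Two programmers could each claim to follow the SAP, one applying the formula in 7.2.4.2 and the other applying Section 6, and report different rates from the same data. The rate is also repeated for every effectiveness factor in Section 4.5. Identifying factors that affect effectiveness is a stated objective (Protocol Section 1, SAP 1.2), and a factor related only to the completeness of ratings could look like such a factor.

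**Working it through.** The documents state no response rate, number of cases or unrated share, so there is no planned figure to reproduce. The structure can be checked exactly. The sizes below rest on assumed inputs.

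**Notation.** E = eligible cases (SAP 4.3); I = cases rated indeterminable (code 9); m = eligible cases with no clinical rating; R = markedly improved plus improved.

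**Formulas.**
- As written in 7.2.4.2: R / (E − I).
- Rated cases only (codes 1 to 5): R / (E − I − m).
- With f = m / (E − I), the unrated share of non-indeterminable cases: literal rate = rated-only rate × (1 − f).

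When f = 0 the two agree. For any f above 0 and any R above 0, the literal rate is lower.

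**Reported rate under the literal formula (assumed inputs).**

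| Rated-only rate | f = 0% | f = 5% | f = 10% | f = 20% |
|---|---|---|---|---|
| 50% | 50.0% | 47.5% | 45.0% | 40.0% |
| 70% | 70.0% | 66.5% | 63.0% | 56.0% |
| 90% | 90.0% | 85.5% | 81.0% | 72.0% |

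For example, 0.70 × (1 − 0.10) = 0.63.

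**Effect on the interval.** Take E − I = 100, m = 10 and R = 63, with exact (Clopper-Pearson) two-sided 95% limits, in line with the exact method in SAP 7.1.3:
- Rated only: 63/90 = 70.0% (59.4 to 79.2).
- Literal: 63/100 = 63.0% (52.8 to 72.4).

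The true outcomes of the 10 unrated cases are unknown. If none responded, the rate over all 100 would be 63/100 = 63.0%. If all responded, it would be 73/100 = 73.0%. The literal formula always reports the lower bound.

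**Effect on subgroups.** Take two subgroups with the same 70% rated-only rate, one with 5% unrated and the other with 20%. The formula gives 0.70 × 0.95 = 66.5% and 0.70 × 0.80 = 56.0%, a gap of 10.5 percentage points that comes only from the difference in unrated shares.

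**The case against.** The strongest reply is that Section 6 already settles the matter. Keeping an unrated case in the denominator amounts to imputing non-response, which Section 6 rules out, so a reader of the whole SAP would drop such cases. This is good evidence of intent. But Section 6 says nothing about denominators, and 7.2.4.2 gives an explicit formula that subtracts one group only. The likely intent is a reason to correct the formula; it does not change what the formula says.

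The pattern may also be rare. Section 5.2.2 says a clinical rating will be made, code 9 is available when the physician cannot judge, and the CRO can query blank fields (Protocol Section 4). Nothing in the documents shows that patients with bacteriology but no clinical rating are expected. That stands. With only 1% or 2% unrated, a 70% rate would become 69.3% or 68.6%. The 5% to 20% shares used above are illustrations, not estimates.

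The different wording in 7.2.4.3 may simply reflect its separate analysis set. That is possible, but it leaves clinical efficacy with neither its own set nor an evaluated-cases denominator.

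A reader could also compare the category counts required by 7.2.4.2 with the denominator and notice the shortfall. That is possible for the overall rate, but no line for unrated cases is planned, and 7.2.4.4 does not ask for category counts by subgroup.

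Finally, a rated-only rate is itself unbiased only if being unrated is unrelated to outcome. This is correct, and it is why the unrated count should be shown beside the rate.

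**Conclusion.** The concern holds. As written, both denominators in 7.2.4.2 include eligible cases or patients with no clinical rating, and these can only lower the rate. This is inconsistent with Section 6 and with the treatment of the eradication rate in 7.2.4.3. The reduction is a factor of one minus the unrated share: nothing if every course is rated, and 7 percentage points in the example with a 70% rated-only rate and 10% unrated. The actual unrated share is not in the documents, so the practical size is unknown. The analyses are exploratory, with no significance level and no decision rule (SAP 3.1 and 3.2). What is affected is therefore the reported rate, its interval and the subgroup comparisons, not a confirmatory test. The change should be made, but it matters only if unrated cases occur.

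**What to change.** 1. In both formulas of SAP 7.2.4.2, define the denominator as cases (or patients at the final observation point) evaluated for clinical efficacy except indeterminable, that is, those rated 1 to 5. This matches 7.2.4.3 and Section 6.
2. State that the subgroup analyses in 7.2.4.4 use the same denominator.
3. Report the numbers of unrated and of indeterminable cases beside each clinical response rate, including within subgroups.
4. Optionally, add a sensitivity row that counts unrated and indeterminable cases as non-responders, so that the reader sees how far the rate depends on them.

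The cost is one phrase in each of two formulas and two counts in an existing table. No new data are needed.
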